Participants randomized to the Patient Choice between facilitated DOT and facilitated SAT arm will be offered a choice between arms 1 and 2. A research nurse will review each section of the decision aid with participants, discuss values and preferences, and, after addressing any questions, ask participants to select facilitated DOT or facilitated SAT. Participants will have the option to switch between DOT and SAT at any time. The reason for switching and time spent under each strategy will be recorded.

Eligibility Criteria

To be included in the randomized trial, patients will have to meet all of the following inclusion criteria and none of the exclusion criteria:

1. Inclusion Criteria:

- a. HIV-positive client engaged in care at the Mulago ISS clinic
- b. Weight $\geq 40\text{kg}$
- c. Age 18 years or older
- d. Capacity to provide informed consent in English or Luganda

(From our experience conducting similar studies at the Mulago ISS clinic, the majority of patients receiving care at the clinic are able to communicate using the Luganda language. For example, while

conducting patient Knowledge, Attitudes and Practices (KAP) interviews during the formative phase, 21/25 (84%) participants opted for Luganda and only four of the 25 opted for English as the language for the interview. Therefore, in addition to Luganda, we selected English as the other preferred language for the study)

2. **Exclusion Criteria:**

- a. Suspicion of active TB based on positive WHO symptom screen AND elevated POC CRP, or current or planned TB treatment
- b. Actively taking an antiretroviral medication contraindicated for use with rifapentine under contemporary WHO or Ugandan policy
- c. Contact of a TB patient with known resistance to isoniazid or rifamycins
- d. Women who are pregnant, breast feeding or intending to get pregnant in the next 120 days. Note: women who become pregnant while on 3HP will be recommended to continue and complete 3HP treatment per Uganda 2020 Uganda National Guidelines, and will be monitored for side effects as per the study protocol ²⁶
- e. Prisoners
- f. Previously completed treatment for active TB or at least 6 months of isoniazid preventive therapy within past 2 years
- g. Not intending to remain within 25 km of the Mulago ISS clinic during the study period or to receive further care at the Mulago ISS clinic
- h. Lack of access to a mobile telephone or lack of willingness to receive SMS reminders/IVR phone calls

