After addressing any questions, the research nurse will ask if the client is willing to initiate 3HP (and also the mode of delivery if the client is in the choice arm). The research nurse will then review the details of the 3HP delivery strategy to which the client has been randomly assigned or chosen (if randomized to the choice arm). For SAT, this will include information on how to store 3HP medications, how to properly take 3HP medication each week, how to make phone calls each week to confirm dosing, how to respond to IVR phone call/SMS messages, how to recognize and report side effects and potential adverse events, and when to return for the refill visit. For DOT, this will include information on when and where to come for DOT visits each week, IVR phone call reminders for weekly clinic visits and how to recognize and report side effects and potential adverse events. Of note, participants who decline to initiate 3HP after randomization will be counted as not accepting/completing treatment in the primary (intent-to-treat) analysis and will be followed over time for clinical outcomes.

3. **Survey 1:** A research nurse will administer a survey to all participants to assess a) uptake of key messages delivered as part of standardized counseling about TB preventive therapy and b) costs associated with accessing the clinic. Cost data collection will be based on the WHO handbook for TB patient costing surveys, which includes family and coping costs, and which we have adapted and used in Uganda.²⁷

4. **Survey 2:** Participants randomized to the choice arm will be administered a brief questionnaire to document reasons for their choice of delivery strategy.

5. **Medication administration:** Regardless of study arm, all participants will be referred to the Mulago ISS clinic pharmacy technician after completion of the above research activities to take their first dose of 3HP under direct observation. The pharmacy technician will record the time and date of medication ingestion in the clinic 3HP dosing register.

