^a 3HP treatment may last up to 16 weeks^b Patients randomized to choice arm only^c Time-and-motion studies will be performed on 40 randomly selected days (one day per week throughout the year, stratified by day of week). We anticipate that this will capture up to 250 unique participant visits per arm (750 total).^d Patient costing surveys will include 50 participants from each arm, or 150 participants total^e Only if symptomatic, except at end of follow-up.^f 24 participants/arm

Outcome Measures

Primary Outcome (Effectiveness of delivery options)

Outcome	Numerator	Denominator
Proportion accepting and completing 3HP treatment	Number who take at least 11 of 12 doses within 16 weeks of treatment initiation	Number randomized

Secondary Outcomes (Quantitative)

Outcome	Numerator	Denominator
REACH		
Treatment acceptance	Number taking at least one dose of 3HP	Number randomized
EFFECTIVENESS		
Treatment completion	Number who take at least 11 of 12 doses within 16 weeks of treatment initiation	Number taking at least one dose of 3HP

Cost-effectiveness (overall)	(Cost in Arm A – cost in Arm B) from societal perspective	(DALYs averted in Arm A – DALYs averted in Arm B) from societal perspective
Cost-effectiveness (health system)	As above, but from health system/provider perspective	As above, but from health system/provider perspective
Cost-effectiveness (patient)	As above, but from patient perspective	As above, but from patient perspective
Safety	Number for whom treatment discontinued due to adverse events or intolerance.	Number taking at least one dose of 3HP
Cumulative incidence of TB at 16 months	Number diagnosed with TB during 16-month follow-up	Risk set*
Cumulative incidence of TB at 28 months	Number diagnosed with TB during 28-month follow-up	Risk set*
ADOPTION		
All Participants		
Visit Cost Reimbursement	Number of visits for which reimbursement provided on same day	Total number of DOT/refill visits
Time to complete clinic visit	Mean and median number of minutes for each DOT/refill visit	--
SMS or IVR phone call reminders delivered	Number of SMS or IVR phone call dosing or clinic visit reminders delivered	Total number of SMS reminders scheduled to be sent
SMS or IVR phone call reminders following missed appointments	Number of SMS or IVR phone call dosing or clinic missed appointment reminders delivered	Number of participant weeks with 3HP missed appointments
Screening for active TB	Number screened for active TB during DOT visits	Total number of DOT visits

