- **Primary outcome** analysis will include: 1) unadjusted intent-to-treat comparisons of effectiveness between arms and 2) simple calculation (using the exact binomial confidence intervals) of the effectiveness of each delivery option, with a target of 80%. In these analyses, participants randomized to the choice arm will be treated separately from those randomized to either facilitated DOT or facilitated SAT; the proportion of those in the patient choice arm who choose DOT or SAT will be measured, but the primary outcome will consider all individuals in this arm as randomized to patient choice. Whether 80% acceptance and completion is achieved will be based on the lower bound of the Bonferroni-corrected 98.3% confidence interval exceeding 0.80 in any of the three arms. The intent-to-treat comparisons will use log-binomial regression to calculate prevalence ratios, and Fisher's exact test to determine statistical significance (two-sided alpha of 0.025, including Bonferroni correction). Participants who decline to initiate 3HP after randomization will be counted as not accepting/completing treatment in the primary (intent-to-treat) analysis and will be followed over time for clinical outcomes.
- **Secondary outcome** analysis will include:
 1. **Reach outcomes:** Analysis will include 1) unadjusted comparisons across arms, 2) per protocol analysis of DOT versus SAT in the choice arm in case of crossover including analysis of outcomes among participants who crossed over against outcomes among those who stayed in their originally selected strategy if a sufficiently large number of patients cross over from DOT to SAT or vice versa and 3) simple calculation of the proportion of patients offered 3HP who accept treatment in each arm. We will also compare this outcome across key demographic variables including age, gender, CD4 stratum, and viral load suppression.
 2. **Effectiveness outcomes:** Analysis of effectiveness outcomes will include the development of TB and the occurrence of adverse events analyzed with Chi-square tests, logistic regression, Kaplan-Meier curves, log-rank tests, and Cox regression methods as appropriate. Any signs or symptoms lasting ≥ 3 days duration (by patient self-report) during the previous month will be recorded and included in our analysis. We will also compare outcomes across key demographic variables including age and gender.

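### The choice-arm comparison of participants who crossed over with those who stayed, listed under Reach, says nothing about Reach, and read as completion it cannot be interpreted because of immortal-time bias and confounding by prognosis.

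*Protocol*

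**What the plan says.** Protocol IV, Statistical Considerations, Data Analysis, item 1 of the secondary outcomes (Reach), includes a per-protocol look at DOT versus SAT within the choice arm. Part of it is an "analysis of outcomes among participants who crossed over against outcomes among those who stayed in their originally selected strategy", to be run "if a sufficiently large number of patients cross over from DOT to SAT or vice versa". Neither the outcomes nor the number is defined, and nothing is said about when a switch occurs.

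The related provisions are these:

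- **Reach outcome** (Outcome Measures table): the numerator is "Number taking at least one dose of 3HP", over the number randomized.
- **Completion** (same table): "Number who take at least 11 of 12 doses within 16 weeks of treatment initiation".
- **Day 1** (Study Procedures): in pre-treatment counseling "the research nurse will ask if the client is willing to initiate 3HP", and the mode of delivery is chosen then. Afterwards "all participants will be referred to the Mulago ISS clinic pharmacy technician after completion of the above research activities to take their first dose" under observation.
- **Switching** (Study Arms, Arm 3): "Participants will have the option to switch between DOT and SAT at any time". Also, "The reason for switching and time spent under each strategy will be recorded".

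SAP 3.7 gives two Reach analyses: unadjusted comparisons across arms, and the proportion accepting in each arm. The crossover comparison is not there. SAP 2.3 gives the SAP precedence over the protocol.

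**The concern.** There are two problems, depending on what outcome is meant.

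If it is acceptance, the order of events defeats the comparison. Anyone who changes delivery mode on treatment has already taken a first dose, so every switcher has accepted by definition.

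If it is completion, the groups are formed by an event after baseline that only people still on treatment can experience. A participant who stops after dose 2 is a stayer and a failure. A participant who switches at dose 8 has already persisted for eight doses. The switchers have been selected for persistence whether or not switching does anything.

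The option to switch is built into the choice strategy, and this is the only explicit switcher-versus-stayer contrast planned. A reader could take its result as evidence for or against letting patients switch.

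**Working it through.** The documents give no figure for this comparison, so there is none to reproduce. Switching rates and patterns below are assumptions.

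**Step 1. Reach.** Acceptance among switchers is 100% by construction. Among stayers it is also 100% if only initiators are counted. If decliners count as stayers, the figure only reflects the overall acceptance rate. Using the 91.3% never-switched share from step 2:

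- 95% acceptance: (0.95 × 0.9132) / (0.95 × 0.9132 + 0.05) = 94.6%
- 90% acceptance: (0.90 × 0.9132) / (0.90 × 0.9132 + 0.10) = 89.2%

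Neither figure says anything about switching.

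**Step 2. Completion, with no effect of switching.** Let C be completion among initiators. Participants may stop after each of doses 1 to 10 with constant hazard h, so (1 − h)^10 = C. Those still on treatment switch with weekly probability s, regardless of prognosis. Within a week, switching may come before or after stopping. With switching first and q = (1 − h)(1 − s):

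- Complete, never switched: A = C(1 − s)^10
- Never switched: N = A + h(1 − s)(1 − q^10)/(1 − q)
- Completion in stayers: A/N
- Completion in switchers: (C − A)/(1 − N)

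If stopping comes first, the factor (1 − s) in the second term of N drops out.

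Take C = 0.80, the protocol's target, and s = 0.01:

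- h = 1 − 0.80^0.1 = 0.0221; q = 0.9682; q^10 = 0.7235
- A = 0.80 × 0.9044 = 0.7235
- N = 0.7235 + 0.0221 × 0.99 × 8.682 = 0.9132
- Stayers: 0.7235/0.9132 = 79.2%
- Switchers: (0.80 − 0.7235)/(1 − 0.9132) = 88.1%
- Gap +8.9 points, with about 48 of 552 switching (0.0868 × 552)

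Gaps in percentage points, switching first / stopping first:

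| Completion | s = 0.5% | s = 1% | s = 2% | s = 5% |
|---|---|---|---|---|
| 70% | 12.1 / 15.2 | 12.5 / 15.7 | 13.4 / 16.8 | 16.2 / 20.3 |
| 80% | 8.6 / 10.6 | 8.9 / 11.0 | 9.5 / 11.9 | 11.8 / 14.7 |
| 90% | 4.5 / 5.5 | 4.7 / 5.8 | 5.0 / 6.2 | 6.4 / 7.9 |

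For s from 0.5% to 2% (roughly 4% to 17% of participants switching), the gap is about 9 to 12 points at 80% completion and about 5 to 17 points over 90% to 70%. At s = 5%, where over a third switch, it is larger.

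**Step 3. Early switching.** Same null model at 80% completion, 10% cumulative switching, switches confined to the first doses. The gap is about 2 points if all switches occur by dose 2, 3 by dose 3, 4 by dose 4 and 6 by dose 6.

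**Step 4. Switching related to prognosis.** At 80% completion, switching first, suppose 30% of participants are strugglers with higher stopping and switching hazards than the rest, whose weekly switching is s = 1%. Switching still has no effect.

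| Stopping multiple | Switching multiple | Gap (points) |
|---|---|---|
| 3 | 3 | +5.2 |
| 5 | 5 | +0.2 |
| 8 | 5 | −2.1 |
| 5 | 10 | −4.6 |
| 8 | 10 | −8.3 |

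**Step 5. Landmark check.** Take those still on treatment at dose 6 and classify them by switch status at that point. Under the model of step 2, later completion is 0.80^(5/10) = 89.4% in both groups. The timing artefact is gone; confounding by prognosis would remain.

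**The case against.** The strongest reply concerns status. The SAP takes precedence, and its Reach analysis omits the comparison, so deleting it would only bring the protocol into line. That stands, and it limits the consequence. But the SAP does not expressly withdraw the comparison: SAP 2.4 refers to the protocol for the full description of secondary outcomes. The protocol under review, which carries 28-month TB outcomes that the SAP lacks, still states it.

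Second, the protocol never says that the outcomes are completion. That also stands, so the completion half of this point is conditional on that reading.

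Third, a reader might infer from step 2 that the analysis would show switchers completing more often. The documents do not support that. They give no rate, timing or determinants of switching; early switching shrinks the gap, and switching by people already likely to stop can cancel or reverse it.

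Fourth, a reader might infer that the trial would reach a false conclusion about choice. It would not on this account: the primary intention-to-treat analysis counts everyone in the choice arm as choice, whether or not they switch. Nor is the trial's 10-point minimum important difference a formal yardstick here, since it was set for randomized choice versus DOT.

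Finally, the protocol names inverse probability weighting for its per-protocol and as-treated completion analyses, which shows awareness of such bias. It does not attach weighting to this contrast. The as-treated analysis in SAP 3.5 compares DOT with SAT and has no rule for people who switch.

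**Conclusion.** The point holds in a limited form. That the comparison cannot inform Reach follows from the order of events on Day 1 and needs no assumed rate. Read as completion, it has immortal-time bias of the size shown in step 2 when switching is inert, unrelated to prognosis and evenly spread. Under the other patterns examined, the null gap ranged down to about −8 points. A contrast that can fall anywhere in that range with no true effect is uninterpretable, and its net direction cannot be predicted from the documents. The consequence is confined to a conditional, secondary protocol analysis outside the SAP's list.

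**What to change.** Delete the crossed-over versus stayed comparison from the protocol's Reach analyses, so that they match SAP 3.7.

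If the question is worth keeping, move it to treatment completion in both documents, as exploratory and explicitly non-causal, in one of two forms:

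- switching as a time-varying exposure, comparing the hazard of stopping after and before a switch; or
- a landmark: among choice-arm participants still on treatment at a fixed dose, later completion by switch status at that point.

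Either form should adjust for adherence up to that point. A fixed minimum number of switchers in place of the open-ended condition would be tidy but is optional.

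The cost is a wording change and a little more analysis. No new data are needed: time under each strategy is recorded (Protocol, Arm 3), and dose dates are in the adherence database (SAP 3.2). The landmark loses a little precision because early stoppers drop out of it.

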Participants randomized to the facilitated DOT arm will attend the Mulago ISS clinic on a weekly basis to ingest 3HP medication under direct observation. DOT will be defined as a designated clinic staff member observing ingestion of each dose of 3HP. Additionally, participants randomized to facilitated DOT will receive:

1. DOT cards with instructions to present directly to the pharmacy for a pharmacy-only visit, without the need to wait in the general queue.
2. Automated SMS or interactive voice response (IVR) phone call reminders at no cost to participants the day before each appointment.
3. A fixed level of reimbursement (~\$5-8/visit) for each weekly visit, conditional on either directly observed therapy or evidence of an adverse event that would preclude further treatment.

Participants who fail to return for a scheduled appointment within 24 hours will receive an SMS or IVR phone call reminder for three consecutive days after the missed appointment.

Arm 2: Facilitated SAT

Participants randomized to the facilitated SAT arm will take their first dose of medication under direct observation and be provided with a 4-week supply of 3HP to take weekly via self-administration. Participants will be asked to return to the Mulago ISS clinic after completing their 5th dose to review adherence data with the Mulago ISS clinic pharmacy technician and receive 5 additional doses of 3HP (doses 7-11). At the scheduled refill visit (dose 6) and the end-of-treatment visit (dose 12), participants will ingest 3HP doses under direct observation. Additionally, participants will receive:

1. 99DOTS-based digital adherence technology to monitor and promote adherence.
2. Weekly check-ins via two-way SMS or IVR phone call for dosing reminders and messaging asking "Are you well?" (or other similar message, as determined in our formative research phase), to serve as an alternative to weekly visits with a health worker to inquire about potential side effects
3. A fixed level of reimbursement (~\$5-8/visit) for the refill and end-of-treatment visit, conditional on either directly observed therapy or evidence of an adverse event that would preclude further treatment.

Participants who fail to return for a scheduled appointment within 24 hours will receive an SMS or IVR phone call reminder for three consecutive days after the missed appointment.

Arm 3: Patient Choice between facilitated DOT and facilitated SAT

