 - a. **All participants:** A standardized checklist-based survey will be used to assess for symptoms of hepatotoxicity or other adverse events (e.g., rash, peripheral neuropathy). The Mulago ISS clinic pharmacy technician will administer the survey at each scheduled clinic visit and at any unscheduled clinic visits if participants present due to concerns about toxicity. Participants with potential adverse events based on the survey will be referred to Mulago ISS clinic clinicians, who will make all decisions regarding further evaluation and treatment continuation or discontinuation. For those with potential symptoms of hepatotoxicity (e.g., abdominal pain, nausea, vomiting, unexplained fatigue or jaundice) this could include a blood draw to assess for elevated liver function tests. Note: women who become pregnant while on 3HP will be recommended to continue and complete 3HP treatment, and will be monitored for side effects as per routine procedures.
 - b. **Facilitated SAT:** In lieu of weekly clinic visits, participants taking 3HP by Facilitated SAT will receive a weekly free (at no cost to them), automated SMS check-in message or IVR phone call asking "Are you well?" (or other similar message, as determined in our formative research phase) with previous instruction to respond "Yes" or "No". All incoming SMS messages will be automatically reimbursed. The Mulago ISS clinic pharmacy technician will receive an automated SMS when a participant responds "No" or does not respond within 24 hours and will call the participant up to three times and ascertain whether he or she is having side effects using the standardized checklist-based survey. Participants who are unable to be contacted by phone will be visited at home by a community health worker (**CHW**). Participants with potential adverse events based on the survey will be referred to Mulago ISS clinic clinicians, who will make all decisions regarding further evaluation and treatment continuation or discontinuation. For those with potential symptoms of hepatotoxicity (e.g., abdominal pain, nausea, vomiting, unexplained fatigue or jaundice) this could include a blood draw to assess for elevated liver function tests.

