3. **Active TB assessment:** The pharmacy technician will perform symptom screening using the Mulago ISS clinic intensified case finding form, and refer symptomatic patients to Mulago ISS clinicians for further evaluation. The clinician will make all decisions regarding TB testing, initiation of TB treatment, and continuation/discontinuation of 3HP.
4. **Medication administration:**

- a. **Facilitated DOT:** For all scheduled visits, medications will be prepared in advance. The pharmacy technician will address any patient questions about treatment, confirm continued interest in taking medications, provide INH and RPT tablets (as loose pills or fixed dose combination pills), with or without pyridoxine, and observe medication ingestion.
- b. **Facilitated SAT participants:** At weeks 6 and 12, participants will return to the Mulago ISS clinic. The pharmacy technician will address any patient questions about treatment, confirm continued interest in taking medications, provide INH and RPT tablets (as loose pills or fixed dose combination pills), with or without pyridoxine, and observe medication ingestion. At the week 6 visit, the technician will also provide additional doses of 3HP until the end-of-treatment visit and remind the patient about side effects.

5. **Participant reimbursement:** At each visit, the pharmacy technician will give DOT participants cash reimbursement for expenses related to transportation and food. SAT participants will be reimbursed at the same fixed level as DOT participants but only at their refill visit at week 6 and end-of-treatment visit at Week 12. A fixed level of reimbursement will be determined in our formative assessment and based off of current local transportation costs [which have doubled during the COVID pandemic] but will total approximately US\$5-8 (15,000-30,000 USh) per visit. Receipt of this reimbursement will be conditional on either directly observed therapy or evidence of an adverse event that would preclude further treatment.

The following *study-specific activities* will be performed by research staff during 3HP DOT or refill visits:

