2. **In-depth Interviews:** will be conducted with patients to identify processes and contextual factors that influenced patient's acceptance and completion of 3HP under each delivery strategy. For each of the three delivery strategies, 24 participants (72 in total) will be purposively sampled to include those who completed all 12 doses, those who only completed the doses after being reminded for 3 days after missing the originally scheduled dose and those who failed to complete the doses despite the reminders on the day before and 3 days after the missed dose or clinic appointment. The interviews will be conducted in either English or Luganda depending on the participants' preference. The interviews will be audio recorded and later transcribed in readiness for analysis. Transcripts for interviews conducted in Luganda will be translated to English.
3. **Key Informant Interviews** will be conducted with health service providers to identify clinic-level facilitators and barriers to adoption and implementation of 3HP under each delivery strategy. Participants for the key informant interviews will be purposively sampled based on their cadres (*e.g.* Doctors, Clinical officers, Pharmacists, Pharmacy technicians, Nurses, Counselors, Peer educators and administrators) and on their involvement in the delivery of 3HP. Up to 10 providers (N=10) will be selected to take part in the key informant interviews. Key informant interviews will be conducted mainly in English by trained staff, audio-recorded and professionally transcribed.

Table 2. Participant data collection and measurements.

Procedure	Day 1	Weekly (DOT) or 6-week refill visit (SAT) during 3HP treatment (Weeks 2-11) ^a	Post-3HP treatment	
			Week 12 ^a	Every 2-3 Months (Months 3-28) ^a

Baseline questionnaire - Demographic and clinical information	X			
Survey 1 - Cost (to access clinic) - Knowledge/Beliefs/Support	X			
Survey 2^b - Reasons for choice	X			
Time-and-Motion studies^c		X		
Patient costing survey^d		X		
3HP adherence assessment		X	X	
Adverse events assessment		X	X	
Active TB assessment^e		X	X	X
3HP delivery process metrics		X		
Survey 3 - Satisfaction with care			X	
In-depth interview^f			X	

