### 3.7 Analysis of secondary outcomes

Secondary outcome analysis will include:

1. **Reach outcome(s):** 1) Unadjusted comparisons across arms, and 2) simple calculation of the proportion of patients randomized who accept treatment in each arm.
2. **Effectiveness outcomes:** 1) Occurrence of AEs across arms will be assessed using Chi-square tests and logistic regression; 2) Incidence of active TB will be assessed using Kaplan-Meier curves, log-rank tests, and Cox proportional hazards methods as appropriate. Assessment for active TB occurs at 15-16 months post enrolment. Survival analyses will include:
  - o An assessment of the incidence rate of TB, comparing across arms (DOT vs. SAT vs. Choice) using Kaplan Meier, time-to-event analyses. We will estimate the difference in the Kaplan Meier and Cox proportional hazard estimators for the survivor functions, comparing the arms to get hazard ratios and 95% CIs.
  - o An assessment of the incidence rate per arm by drug compliance, which will include for each arm: a comparison of the incidence of active TB in those within the arm that complete at least 11 of the 12 doses within the allotted 16 weeks vs. the incidence of active TB in those within the arm that complete  $\leq$ 10 doses of 3HP. We will estimate the difference in the Kaplan Meier and Cox proportional hazard estimators for the survivor functions, comparing the arms to get hazard ratios and 95% CIs.

3. **Adoption outcomes:** For each process metric, we will report the monthly proportion (and 95% CI) number, or median (interquartile range (IQR)) to assess the implementation of intervention components in each arm.
4. **Implementation outcomes:** Quantitative data will be assessed using multivariable regression models to compare by study arm patient survey data including a) patient costs; b) scores on questions related to patient barriers to TB preventative care; and c) patient satisfaction. Qualitative data will be analysed using appropriate software where open coding will be applied to generate codes and themes. Thematic groupings will be developed and reviewed to identify emergent themes within each domain of the coding framework and quotes that best represent each domain. Thematic interpretation will include collaborative development of a coding framework and detailed coding of transcripts.

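### One-month symptom recall with no onset rule and no checklist before dose 1 can count pre-treatment symptoms as adverse events, more routinely under DOT than under SAT

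*Protocol*

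**What the plan says.** The rule is in the protocol, section IV, Statistical Considerations, Data Analysis, under Effectiveness outcomes: "Any signs or symptoms lasting ≥ 3 days duration (by patient self-report) during the previous month will be recorded and included in our analysis". SAP 3.7, item 2, states the comparison: "Occurrence of AEs across arms will be assessed using Chi-square tests and logistic regression". SAP 2.3 gives the SAP precedence. But SAP 3.7 has no AE definition, recall period or baseline rule, so the protocol sentence is the only inclusion rule for symptoms.

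The instrument is described under Adverse events screening. Item a, for all participants, sets a standardized symptom checklist: "The Mulago ISS clinic pharmacy technician will administer the survey at each scheduled clinic visit and at any unscheduled clinic visits" when toxicity is the concern. The number of scheduled visits depends on delivery mode. DOT participants "will attend the Mulago ISS clinic on a weekly basis to ingest 3HP medication under direct observation". For SAT, "At weeks 6 and 12, participants will return to the Mulago ISS clinic". Item b adds: "In lieu of weekly clinic visits, participants taking 3HP by Facilitated SAT will receive a weekly free" automated message or call asking whether they are well. A negative answer, or no reply within 24 hours, leads to telephone calls that use the same checklist.

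On Day 1, "all participants will be referred to the Mulago ISS clinic pharmacy technician after completion of the above research activities to take their first dose". Those research activities are a baseline questionnaire, counseling and surveys; no AE checklist is among them. In Table 2 the row "Adverse events assessment" is marked for the on-treatment visits (Weeks 2-11) and Week 12, with nothing under Day 1.

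**The concern.** A treatment-emergent event is normally one that starts or worsens after the first dose. This plan has neither an onset condition nor a scheduled pre-dose checklist to compare against. A one-month recall used one week after dose 1 asks mostly about time before treatment; the same recall used at Week 6 does not. Delivery mode sets when the checklist is routinely given, so it also sets how much pre-treatment time is routinely searched. An excess of AEs under DOT could then be partly a product of the recall window, and the chi-square and logistic analyses could not separate this from a real difference.

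Pre-existing symptoms are plausible in this population. Exclusion criterion (a) removes people with a positive TB symptom screen only if C-reactive protein is also elevated (or TB treatment is current or planned), so some symptomatic people can enroll. Several checklist symptoms, such as nausea, fatigue and abdominal pain, are non-specific.

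**Working it through.** The documents give no figure to reproduce here; the check is calendar arithmetic.

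**Inputs**
- Dose 1 on Day 1 in all arms, taken as day 0 (Study Procedures, Medication administration).
- DOT visits weekly, so the Week w visit falls 7(w − 1) days after dose 1: 7, 14, 21, 28, 35, ..., 77.
- SAT scheduled visits at Week 6 (day 35) and Week 12 (day 77).
- Recall length M: one month, not defined in days. Assumed range 28, 30 and 31.
- Premise: the one-month recall is used at each scheduled checklist. The rule names no instrument or visit, so this is inferred.

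**Pre-dose days in the window** = max(0, M − 7(w − 1))

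| Visit | M = 28 | M = 30 | M = 31 |
|---|---|---|---|
| DOT Week 2 (day 7) | 21 | 23 | 24 |
| DOT Week 3 (day 14) | 14 | 16 | 17 |
| DOT Week 4 (day 21) | 7 | 9 | 10 |
| DOT Week 5 (day 28) | 0 | 2 | 3 |
| DOT Week 6 onward | 0 | 0 | 0 |
| SAT Week 6 (day 35) | 0 | 0 | 0 |
| SAT Week 12 (day 77) | 0 | 0 | 0 |

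The window reaches before dose 1 at three DOT visits if M = 28 and at four if M = 30 or 31. A complete 3-day episode lying wholly before dose 1 fits at three visits (M = 28 or 30) or four (M = 31).

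**SAT windows.** At Week 6 the window opens 35 − M = 7, 5 or 4 days after dose 1. At Week 12 it opens 77 − M = 49, 47 or 46 days after. A late visit moves the window further from dose 1, so slippage in the schedule does not bring pre-dose time into these visits.

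**Triggered SAT contacts.** A telephone checklist in Weeks 2 to 5 would reach back as far as the DOT visit of the same week, if the same recall is used. The contrast is therefore routine capture under DOT against triggered capture under SAT.

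**Persistent symptoms.** A symptom already present at dose 1 that lasts at least 3 days into the Week 6 window is recorded at SAT Week 6 as well. At scheduled SAT visits the rule misses only earlier episodes that resolve around dose 1 or in the first days after it.

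**Choice arm.** It mixes both modes and is affected in proportion to the share who choose DOT.

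**The case against.** The strongest case against the point has five parts.

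1. A reader might infer that pre-existing symptoms become AEs under DOT only. The protocol does not support that. Item b of Adverse events screening gives SAT participants the same checklist after a negative or missing reply, item a covers unscheduled visits, and persistent symptoms are picked up at Week 6. This objection stands: the difference is one of degree.
2. The recall sentence names no instrument, the checklist is described with no recall period, and the SAP has no look-back at all. This stands as a limit on the day counts. It does not remove the problem: the checklist is the only AE symptom instrument described, and without an onset condition pre-dose symptoms qualify under any one-month recall used early in treatment.
3. A reader might infer that the tabulated safety outcome, discontinuation for adverse events or intolerance, is inflated. The documents do not show this. Clinic clinicians make those decisions, and reasons come from chart review.
4. Some baseline information exists: a medical history and clinical evaluation, a TB symptom screen, and a questionnaire with clinical information. The forms are not in the documents, so they may hold some usable symptom data. But no AE checklist is scheduled, and no rule tells the analyst to use these data.
5. AE monitoring deliberately follows routine care, and symptom occurrence is not in the outcome table. That limits the importance of the point. It does not excuse a stated between-arm test whose events may predate treatment.

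**Conclusion.** The point holds as a defect in a secondary comparison. Under the plan as written, symptoms that began before treatment can be counted as AEs in every arm, and more routinely under DOT. On the premise that the recall accompanies each scheduled checklist, the first DOT checklist after Day 1 covers 21 to 24 pre-dose days and the scheduled SAT checklists cover none. The AE comparison in SAP 3.7 can therefore be biased toward an excess under DOT; the documents do not show that it will be.

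The size of the between-arm difference cannot be derived. A reader might multiply an assumed symptom prevalence by the 552 per arm. The documents give no prevalence, and the product would be a count of affected DOT participants, not a difference from SAT, where some of the same symptoms are also captured. The primary outcome is not involved.

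**What to change.** 1. In the protocol's Effectiveness outcomes paragraph and in SAP 3.7, item 2, count as AEs only symptoms with onset or worsening after dose 1, and name the instrument and visits to which the recall applies. The cost is wording and slightly fewer counted AEs.
2. For any participants still to be enrolled, give the existing checklist on Day 1 before the first dose in all arms and mark it in Table 2. This takes a few minutes at a visit already held. Table 1 plans trial enrollment and follow-up for 2020-2021, and the current SAP is dated April 2022, so this step may come too late for most or all participants.
3. Add a sensitivity comparison limited to the Week 6 and Week 12 checklists. Both delivery modes have visits then, and the windows match and do not reach before dose 1. Its price is coverage: the two windows span 56, 60 or 62 of the 77 days from dose 1 to Week 12 (M = 28, 30, 31), so 21, 17 or 15 days are lost, including the first 4 to 7 days on treatment. Symptoms that persist from before dose 1 would still count, but through the same windows in all arms.

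The documents do not say that onset dates are collected. Where onset was not recorded for participants already enrolled, only the third step is available.

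Shortening the recall to the time since the previous checklist is not a substitute. It would give DOT about 7 days, and SAT about 35 days up to Week 6 and 77 − 35 = 42 days up to Week 12, which is a new imbalance between modes.
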